4.3 STUDY TREATMENT

4.3.1 Formulation

Ranibizumab is formulated as a sterile solution aseptically filled in a sterile, 3-mL stoppered glass vial. Each single-use vial is designed to deliver 0.05 mL of 10 mg/mL

ranibizumab aqueous solution with 10 mM histidine HCl, 10%, α -trehalose dihydrate, and 0.01% polysorbate 20, pH 5.5. The results in the delivery of a 0.5 mg dose of ranbizumab. Each vial contains no preservative and is suitable for **single use only**.

Further details and molecule characterization will be included in the Investigator Brochure.

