1.1 PATHOPHYSIOLOGY

The current standard of care treatment for diabetic macular edema is anti VEGF therapy. Both 0.3mg Lucentis and Eylea have been shown to be superior to Avastin for treatment of diabetic macular edema in eyes with more advanced edema and poorer vision. 1.(DRCR Protocol T)

While there is a paucity of data of aqueous VEGF levels after Lucentis injection for DME, one study tested aqueous cytokines in response to bevacizumab injection in diabetic macular edema. Costagliola, et. al. demonstrated that aqueous VEGF levels remain lower but are still elevated compared to control patients in response to Avastin injections for DME(2). Based on Lucentis' tighter binding to VEGF (lower k_d) and greater penetration of the retina, we postulate that Lucentis injections will be much more effective at lowering aqueous VEGF levels explaining Lucentis' greater efficacy compared to Avastin in DRCR Protocol T. In the present protocol, we plan to use Lucentis 0.3 mg to demonstrate the VEGF levels will be lower compared to published results of aqueous VEGF levels after Avastin use. Furthermore we have preliminary data from a clinical trial at the Van Andel Institute demonstrating VEGF levels can predict response to anti-VEGF therapy. Clinical response will be measured by ETDRS visual acuity and spectral domain OCT central thickness. Finally, there is evidence that anti-VEGF therapy can normalize the pathologic intraocular environment beyond neutralizing VEGF. It is also well documented that anti VEGF therapy effects not only vascular endothelial growth factor but may also lower other inflammatory cytokines such as IL5, IL10 and interferon alpha. (3. Suzuki, et. al)

The present protocol will measure a number of cytokines in addition to VEGF in response to 0.3mg Lucentis therapy for diabetic macular edema. We have previously demonstrated a large number of cytokines can be measured in a small quantity of ocular fluid using aqueous or vitreous samples with a microbead assay. (4. J.White, L.Glazer, et.al). We propose that use of 0.3mg Lucentis, concurrently with aqueous taps for diabetic macular edema, will

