document lower aqueous VEGF levels compared to other anti VEGF inhibitors (vs that in Costagliola, et. al [2]), will decrease the level of inflammatory cytokines, and will predict clinical response to Lucentis therapy demonstrated by visual acuity and OCT. Finally, showing efficacy with this dose of Lucentis should provide a good rationale for use of 0.3mg Lucentis in further DRCR studies.

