1.2 TREATMENT OF SEVERE DIABETIC MACULAR EDEMA (DISEASE SPECIFIC)

The current best treatment options for these patients include Lucentis 0.3 or 0.5mg or Eylea. Present study will use the 0.3mg dose of Lucentis and perform an anterior chamber tap measuring aqueous cytokines before the first injection of Lucentis and just before the fourth intravitreal injection of 0.3mg Lucentis.

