1.3 RANIBIZUMAB FOR SEVERE DIABETIC MACULAR EDEMA (DISEASE SPECIFIC)

Both Lucentis 0.3mg and 0.5mg dose and Eylea have been shown to be highly effective for severe diabetic macular edema with poor vision. The DRCR Protocol T did not test the 0.5mg dose of Lucentis against Eylea. We believe the 0.3mg dose will be especially effective in patients with recalcitrant diabetic macular edema (with probable markedly elevated VEGF levels.)

A positive result from the current study will give the DRCR and NEI further rationale to test the 0.3mg Lucentis dose in future protocols and also to compare the 0.3mg dose to Eylea.

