2. OBJECTIVES

2.1 Primary Objective

1. Measure aqueous VEGF levels in response to 0.3mg Lucentis dose for diabetic macular edema
2. Measure other cytokines response to 0.3 mg Lucentis dose for diabetic macular edema
3. Correlate clinical response (vision, spectral domain OCT retinal thickness level) to VEGF levels

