4.3.2 Dosage, Administration, and Storage

Dosage

0.3mg Lucentis dose used

b. Administration

Intravitreal injection

c. Storage

Upon receipt, study drug kits should be refrigerated at 2°C - 8°C (36°F - 46°F). DO NOT FREEZE. Do not use beyond the expiration date. Ranibizumab vials should remain refrigerated. Protect vials from direct light. Store in original carton until time of use.

RANIBIZUMAB VIALS ARE FOR SINGLE USE ONLY. Vials used for one subject may not be used for any other subject.

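### The only study vial described (Section 4.3.1) delivers 0.5 mg, the stated study dose (Section 4.3.2) is 0.3 mg, and no concentration and volume given in the protocol yields 0.3 mg

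*Combined protocol and SAP*

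**What the plan says.** Section 4.3.1 (Formulation) describes a single presentation: "Each single-use vial is designed to deliver 0.05 mL of 10 mg/mL" ranibizumab solution. It then states the result: "The results in the delivery of a 0.5 mg dose of ranbizumab".

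Section 4.3.2 (Dosage, Administration, and Storage) says "0.3mg Lucentis dose used". It adds the intravitreal route and the storage conditions, but no injection volume, product strength or preparation step.

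Elsewhere the study dose is consistently 0.3 mg:
- Section 1.1: "we plan to use Lucentis 0.3 mg to demonstrate the VEGF levels will be lower".
- Section 1.2: "Present study will use the 0.3mg dose of Lucentis".
- Section 2.1, objective 1: "Measure aqueous VEGF levels in response to 0.3mg Lucentis dose for diabetic macular edema". Objective 2 names the same dose for the other cytokines; objective 3 names none.
- Sections 5.3, 5.6.2 and 5.6.5 identify the study drug by the 0.3 mg strength in the causality, post-study and IND reporting rules.

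The other mentions of 0.5 mg, in Sections 1.2, 1.3 and 1.5, are background on treatment options and earlier studies. None describes an arm of this trial.

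**The concern.** This is a ten-patient study of one drug, and dose defines the exposure whose effect is measured. The treatment section names one dose but describes a product that, used as designed, delivers another. Nothing in the protocol tells the injector how to get from the vial to the named dose.

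Two consequences follow if the described vial is supplied and its full volume injected. First, the primary results would be attributed to a dose not given. The protocol means to use them as dose-specific evidence: Section 1.1 says that showing efficacy "should provide a good rationale for use of 0.3mg Lucentis in further DRCR studies", and Section 1.3 says that a positive result gives "further rationale to test the 0.3mg Lucentis dose in future protocols". Second, Section 5.6.2 requires special situation reports for overdose, erroneous administration and medication error. Those rules need a clear reference dose and volume, and the text does not give the volume.

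The concern is with dose attribution. It makes no claim of excess harm: Section 1.2 lists both strengths among current options, and the large safety study summarised in Section 1.5, in a different disease, found ocular event rates unrelated to dose. It also makes no claim about the size of any effect on measured VEGF.

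**Working it through.** **Inputs.** Concentration 10 mg/mL and volume 0.05 mL (Section 4.3.1); delivered dose 0.5 mg (Section 4.3.1); study dose 0.3 mg (Section 4.3.2); visits at Day 1 and Weeks 4, 8 and 12 (Appendix A); human intravitreal half-life 7 to 8 days (Section 1.4.1).

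**Step 1: reproduce the plan's figure.** Dose = concentration × volume = 10 mg/mL × 0.05 mL = 0.5 mg. This matches Section 4.3.1 exactly, so that section is consistent with itself.

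**Step 2: compare with Section 4.3.2.** Ratio 0.5 / 0.3 = 1.67. Difference 0.5 − 0.3 = 0.2 mg per injection.

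**Step 3: look for a pair that gives 0.3 mg.** Holding the stated volume, the concentration would have to be 0.3 / 0.05 = 6 mg/mL. Holding the stated concentration, the volume would have to be 0.3 / 10 = 0.03 mL. Neither figure appears in the protocol. They are used here only to search the text and are not proposals. Section 4.3.1 is the only place that gives a ranibizumab concentration or injection volume. Appendix B covers preparation for the injection and gives neither. Section 6.6 (drug accountability) names no strength.

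**Step 4: amount given before the second aqueous tap, if the full vial volume is used.**

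| Tap timing | Injections before tap | At 0.5 mg | At 0.3 mg | Difference |
|---|---|---|---|---|
| Before the fourth injection (Sections 1.2, 4.5.1) | 3 | 1.5 mg | 0.9 mg | 0.6 mg |
| After the fourth injection (Section 4.8.3) | 4 | 2.0 mg | 1.2 mg | 0.8 mg |

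The two rows exist because the protocol also disagrees with itself on tap timing, which is a separate matter. The ratio is 1.67 in both.

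**Step 5: what these totals mean at the tap.** They are amounts given, not amounts remaining. Assume first-order loss, 28-day spacing and a tap before the fourth injection. The fraction left after one interval is f = 2^(−28 / half-life), and the remaining difference is 0.2 × (f + f² + f³).
- Half-life 7 days: f = 0.0625, so 0.2 × (0.0625 + 0.0039 + 0.0002) = 0.013 mg.
- Half-life 8 days: f = 0.0884, so 0.2 × (0.0884 + 0.0078 + 0.0007) = 0.019 mg.

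The absolute difference left at the tap is small, although the ratio stays at 1.67. The per-injection comparison in Step 2 is the figure to carry forward.

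**The case against.** The strongest reply is that the intended dose is not in doubt. Section 4.3.2 is the only dosing statement, every other place that names this study's dose agrees with it, and Section 4.3.1 describes a vial without instructing the injector. The protocol also carries visible template residue, such as an unfilled day window in Section 4.5.2 and a study-drug placeholder in Section 5.3, so the vial description may simply be unedited boilerplate. Section 4.3.1 refers further product detail to the Investigator Brochure, which may settle the matter. Any harm is conditional, and in a single-arm pilot a uniform mislabel would not unbalance groups.

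Much of this stands. The fault is a conflict between two sections plus a missing injection volume; the multiplication itself is right. The exposure consequence is wholly conditional, and the cumulative totals add little to the per-injection figure. The boilerplate explanation is plausible, but it is an inference.

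It does not remove the problem. The description sits under Study Treatment, covers no other presentation and states a delivered dose. If it is not the study product, the protocol describes no study product. A brochure can add detail but does not cancel a contradiction in the protocol. Nor does the rationale show which statement is the leftover: Section 3.2 argues from the benefit of a higher molar dose, while Section 1.3 argues for 0.3 mg. The absence of a comparison arm does not help either, because the results are interpreted by dose.

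**Conclusion.** The concern holds. Sections 4.3.1 and 4.3.2 cannot both describe what is injected if the vial is used as designed, and no other part of the protocol resolves the conflict. Conditional on the described vial being supplied and its full 0.05 mL injected, each dose would be 0.5 mg against a stated 0.3 mg: 1.67 times, or 0.2 mg more. If the product or volume actually used delivers 0.3 mg, the exposure error is zero and the defect is confined to the text. The documents do not show which case applies; the Investigator Brochure was not available.

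The point must be settled before first dosing, because primary objectives 1 and 2 are defined by dose and the results are meant to support a specific dose in later studies. This conclusion does not say which dose or product description is right.

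**What to change.** Before first dosing, the sponsor should reconcile Sections 4.3.1 and 4.3.2 so that the stated concentration multiplied by the stated injected volume equals the stated dose. The injected volume should be written in Section 4.3.2 or Appendix B. The rationale in Sections 1.3 and 3.2 should then be read against the reconciled text, since one argues for a named strength and the other for a higher molar dose.

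An optional safeguard is a case report form line recording product concentration and injected volume at each injection, so that the dose given can be verified at analysis.

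The cost is protocol wording in two sections (and Appendix B, if the volume is placed there), plus a read-through of the two rationale sections. There is no change to design, sample size or visit schedule.

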4.3.2 Dosage, Administration, and Storage

Dosage

0.3mg Lucentis dose used

b. Administration

Intravitreal injection

c. Storage

Upon receipt, study drug kits should be refrigerated at 2°C - 8°C (36°F - 46°F). DO NOT FREEZE. Do not use beyond the expiration date. Ranibizumab vials should remain refrigerated. Protect vials from direct light. Store in original carton until time of use.

RANIBIZUMAB VIALS ARE FOR SINGLE USE ONLY. Vials used for one subject may not be used for any other subject.

4.4 CONCOMITANT AND EXCLUDED THERAPIES

Standard preinjection betadine given along with lid speculum.

4.5 STUDY ASSESSMENTS

4.5.1 Assessments during the Treatment Period

Patients will be seen once per month, see attached study flow sheet. At visit 0 and at 3 month visit patient will also have an aqueous tap prior to Lucentis injection.

4.5.2 Early Termination Assessments

Subjects who withdraw from the study prior to completion should return for an early termination evaluation **10 days ($\pm X$ days)** following the last injection/study visit for monitoring of all adverse events (serious and

nonserious). The schedule of assessments for early termination is the same as that for the final visit.

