2.2 Secondary Objectives

3. STUDY DESIGN

3.1 DESCRIPTION OF THE STUDY

Lucentis injections are the current standard of care for diabetic macular edema. The only deviation from the standard of care in the current protocol is an aqueous tap before the first Lucentis injection and the fourth Lucentis injection for diabetic macular edema. Such an approach has been shown to be extremely low risk for the patient. In a study from Pfahler et. al, (5), with 578 vitreous taps there were minimal complications. Vitreous taps are considered riskier than aqueous taps.

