3.3 SAFETY PLAN

A current IRB exists with [name] lab at MSU to analyze vitreous specimens. See attached. The study is funded by Genentech, and an IRB will be obtained for the current protocol and material transfer agreement will be consummated with [name] to send the aqueous samples directly to her lab.

Safety concerns, the only deviation from current standard of care in the current protocol is an aqueous tap before the first Lucentis injection and before the fourth Lucentis injection. We have previously conducted a clinical trial similar to this with the Van Andel Institute for macular degeneration without any complications. Furthermore, Pfahler (5) performed more than 578 vitreous taps without significant morbidity, which are considered riskier than aqueous taps. Compachairo et al (7) performed aqueous taps on 59 patients receiving Lucentis without morbidity. This is six times the number of patients proposed in this clinical trial.

3.5 compliance with Laws and Regulations

This study will be conducted in accordance with current U.S. Food and Drug Administration (FDA) Good Clinical Practices (GCPs), and local ethical and legal requirements.

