APPENDIX A

Study Flowchart

	Day 1	Week 4	Week 8	Week 12
• Informed Consent	X			
• Inclusion/Exclusion	X			
• Visual Acuity	X	X	X	X
• Refraction	X			X
• IOP	X	X	X	X
• Dilate	X	X	X	X
• OCT	X	X	X	X
• FA/FP	X			
• Ophthalmic Exam	X	X	X	X
• Aqueous sample	X			X
• Lucentis injection	X	X	X	X
• Study Exit				X
• Pregnancy Test if applicable	X	X	X	X

Include a study flowchart for ease of review and understanding of the study.

Note: General note to entire table here.

- a Footnote.
- b Footnote.
- c Footnote.

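### Read literally, Section 4.5.2 carries the Week 12 aqueous tap (and, less clearly, the injection) into the early-termination visit, and the primary 'after' sample is not defined consistently enough to exclude it outright

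*Combined protocol and SAP*

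**What the plan says.** Section 4.5.2 asks subjects who withdraw early to return 10 days, with a tolerance left as ±X, "following the last injection/study visit for monitoring of all adverse events". It then says "The schedule of assessments for early termination is the same as that for the final visit".

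In Appendix A the only column marked for study exit is Week 12, so that is the final visit. The relevant rows read "Aqueous sample X X" (Day 1 and Week 12) and "Lucentis injection X X X X" (all four visits). The footnotes to the flowchart are unfilled template lines, so none of them exempts an early-termination visit.

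Four other places restrict the taps:

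- Section 1.2: "before the first injection of Lucentis and just before the fourth intravitreal injection of 0.3mg Lucentis".
- Section 3.1: "an aqueous tap before the first Lucentis injection and the fourth Lucentis injection for diabetic macular edema".
- The Safety Plan (numbered 3.3 in the body): "an aqueous tap before the first Lucentis injection and before the fourth Lucentis injection".
- Section 4.5.1: "At visit 0 and at 3 month visit patient will also have an aqueous tap prior to Lucentis injection".

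The primary outcome in 3.3.1 compares levels before and after treatment and names no visit. Section 4.8.3 places the second sample after the fourth injection. Section 4.8.4 uses available cases and imputes nothing. The subject discontinuation section (numbered 4.5 in the body) lists endophthalmitis and pregnancy among possible reasons for stopping.

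**The concern.** Two things are at stake.

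The first is what is done to the subject. Staff who follow 4.5.2 to the letter would take a research tap that the rest of the protocol does not provide for. The Safety Plan argues that the two scheduled taps are the only departure from standard care, and a tap at early termination falls outside that argument. If the injection row is carried over as well, nothing in 4.5.2 exempts a subject stopping for endophthalmitis or pregnancy. Yet Section 1.5 states that ranibizumab is contraindicated in ocular infection, and 4.1.3 excludes pregnant women.

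The second is the primary summary. A tap taken at early termination would differ from a completer's Week 12 sample in time since the last dose and, for those leaving after one or two injections, in number of doses. With at most 10 'after' values, a single such sample is at least a tenth of the summary.

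**Working it through.** The plan gives no figure to reproduce: the sample size of 10 is set by feasibility, with no stated effect size, variability or dropout. The check is therefore a comparison of texts, followed by a rough sizing of the timing difference.

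**Does the tap carry over?** Section 4.5.2 extends the final visit's schedule of assessments. Section 4.5.1, whose title concerns assessments, describes the tap. In the protocol's own usage, then, the tap is an assessment and is carried over. The drug is described under 4.3 as study treatment, so the injection row carries over less clearly.

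**When would the sample fall?** Appendix A marks an injection at every visit, so on schedule the last injection and the last visit are the same day. The sample falls about 10 days after dosing: study day 10, 38 or 66 after one, two or three injections (first injection = day 0), against about day 84 for Week 12.

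**How different is the drug level?** Inputs: human intravitreal half-life h = 7 to 8 days (Section 1.4.1) and injections 28 days apart (Appendix A). Assumptions: first-order decay, and aqueous drug falling in parallel with vitreous drug.

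Residual drug, as a percentage of one dose's initial level = 100 × Σ 2^(−t/h), summed over earlier doses, where t is days since each dose.

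| Sample | t (days) | h = 7 | h = 8 | Ratio to Week 12, h = 7 | Ratio to Week 12, h = 8 |
|---|---|---|---|---|---|
| Week 12, before injection 4 | 28, 56, 84 | 6.67 | 9.69 | 1 | 1 |
| Early termination after 1 dose | 10 | 37.15 | 42.04 | 5.57 | 4.34 |
| After 2 doses | 10, 38 | 39.47 | 45.76 | 5.92 | 4.72 |
| After 3 doses | 10, 38, 66 | 39.62 | 46.09 | 5.94 | 4.76 |

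For example, the Week 12 figure at h = 7 is 100 × (2^−4 + 2^−8 + 2^−12) = 6.25 + 0.39 + 0.02 ≈ 6.67, and the one-dose ratio is 37.15 / 6.67 ≈ 5.57.

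**How likely is the situation?** No dropout rate is stated. If each subject's chance of withdrawing is assumed to be 5%, 10% or 20%, the chance of at least one withdrawal among 10 is 1 − (1 − p)^10 = 40%, 65% or 89%. These are upper limits, because the subject must also attend the visit and be tapped.

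**Do the texts filter the sample out?**

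- 3.3.1 does not: it names no visit.
- 4.8.3 does, but it also rules out the scheduled sample. Under 4.5.1 the Week 12 tap precedes that day's injection, and the subject then exits.
- 1.2 rules out a sample after one or two injections. A sample after three would fit only if an early-termination injection were counted as the fourth.
- 4.5.1 names the 3-month visit, which rules out all three early timings. But it is a collection schedule that 4.5.2 then extends, and it is not stated as an analysis rule.

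**The case against.** The case against is substantial. The early-termination visit is stated to be for adverse-event monitoring, and the open ±X suggests unfinished template text. The four sections that limit the taps agree with one another, so a careful analyst would conclude that the 'after' value is the pre-fourth-injection tap and leave anything else out. Section 4.8.4 deals with missing values and does not tell anyone to substitute an off-schedule sample. All of this stands, and it makes the problem one of wording that conflicts, with the intended answer recoverable by inference. It does not make the wording harmless, because 4.8.3, where the analyst would look first, gives a different timing.

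Three stronger readings are tempting and are not supported:

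- A reader might infer that the plan orders an injection into an infected eye or during pregnancy. The text carries over assessments, not clearly treatment. Section 1.5 states the infection contraindication, and Appendix A marks a pregnancy test, where applicable, at every visit. Section 4.5.2 speaks of subjects who withdraw, so it does not clearly reach those whom the investigator removes.
- A reader might infer that the choice between last injection and last visit creates two clocks, placing samples on either side of the Week 12 trough. That needs a visit without an injection, and Appendix A schedules none. It could arise only as a protocol deviation.
- A reader might infer a bias of known size in the VEGF result. The calculation concerns drug, not VEGF. Section 1.4.1 reports parallel decline only between monkey retina and vitreous, so even the aqueous drug figure rests on an assumption.

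**Conclusion.** The point holds in a limited form. As written, 4.5.2 with Appendix A adds an off-schedule aqueous tap at early termination and, less clearly, an injection. This conflicts with four other sections and is probably unintended. On the planned schedule, modelled residual drug in such a sample is about 4.3 to 5.9 times the Week 12 trough, so it is not interchangeable with a completer's sample. That range rests on first-order decay, a 7-8 day half-life and parallel aqueous and vitreous decline. Neither the size nor the direction of any effect on VEGF can be derived from the documents.

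Exclusion of such a sample can be inferred but is not stated as an analysis rule, and 4.8.3 contradicts the collection schedule. The problem arises only if a subject withdraws early, attends the visit and is tapped; the summary is affected only if that value is then pooled.

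**What to change.** - In 4.5.2 and in a footnote to Appendix A, state that early-termination visits comprise the safety and ophthalmic assessments, with no aqueous tap and no Lucentis injection.
- Replace ±X with a number of days.
- In 3.3.1 and 4.8.3, define the 'after' sample as the Week 12 tap taken before the fourth injection, which also corrects the timing in 4.8.3.
- State that any off-schedule sample is listed separately, with days since the last injection and number of injections received, and kept out of the primary summary.

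This costs a few sentences, one footnote and one variable derived from recorded dates. The sample size does not change. The real cost is that an early withdrawer contributes no 'after' value, so the primary summary may rest on fewer than 10 patients.
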